19.1.1.3 Percentage of Patients with Migraines

Day 1

The percentage of patients with a migraine on the day after first dosing will be derived based on whether the patient filled out the eDiary on Day 1 or not. If the patient filled out the eDiary on Day 1, the patient will have a rate of either 0 or 100 on Day 1 that is, 0 if the patient experienced no migraine on Day 1 and 100 if the patient did experience a migraine on Day 1.

If the patient did not fill out the eDiary on Day 1, the rate for the patient will be imputed as:

100*(Number of MMDs Weeks 1-4/28),

where the number of MMDs for Weeks 1-4 is derived as described in Section 19.1.1.1. Note that if the number of MMDs for Weeks 1-4 is missing for the patient and the patient did not fill out the eDiary on Day 1, the Day 1 rate will be missing.

Similarly, the rate for having a migraine on Day 1 after the Week 12 dosing will be imputed using the MMDs for Weeks 13-16 in case of a missing eDiary report on that day.

19.1.1.4 Migraines/Headaches With Severe Pain Intensity and Headache Episodes/Migraine Attacks

The percentage of migraines and headaches with severe pain intensity is derived based on the derived number of monthly migraine attacks and headache episodes.

A migraine attack is defined as 1 continuously recorded migraine. One attack may result in multiple migraine days. Headache episodes are similarly defined. Headache severity is collected on a 3-point scale, Mild, Moderate and Severe. Migraines and headaches with severe pain intensity are defined as migraine attacks/headache episodes with a reported severity of "Severe".

The following describes the derivation of number of monthly migraine attacks. The derivation of monthly headache episodes follows the same principles.

The derivation of the number of monthly migraine attacks will follow the imputation rules described in Section 19.1.1.1 for MMDs, replacing *Reported Migraine Days* with *Reported Migraine Attacks* everywhere. As an example, the number of monthly migraine attacks for a patient with 14 days or more of eDiary reporting in a 4-week period will be derived as:

28*(Reported Migraine Attacks/Reported eDiary Days)

And for a patient who withdraws due to an adverse event or lack of efficacy within the first 28 days post baseline with less than 14 days of eDiary reporting in the first 4-week period, the number of monthly migraine attacks will be derived as:

$$28*(W*X^{att} + (1 - W)*X_p^{att}),$$

where $W = Reported \ eDiary \ Days/13$, $X^{att} = Reported \ Migraine \ Attacks/Reported \ eDiary \ Days$, and $X_p^{att} = preceding \ Number \ of \ Migraine \ Attacks/28$.

The number of monthly migraines and headaches with severe pain intensity is derived in the same way using only migraine attacks/headache episodes with a reported severity of "Severe".

The percentage of migraines and headaches with severe pain intensity is then calculated as the percentage of migraine attacks/headache episodes with severe pain intensity out of the number of migraine attacks/headache episodes. Patients with no migraine attacks/headache episodes are included with a rate of 0.

The average length of headache episodes and migraine attacks will also be derived and will be based on the number of monthly migraine attacks and headache episodes. The number of monthly hours with headache and migraine will be derived similarly to how the number of monthly migraine attacks and headache episodes are derived, i.e. to derive the monthly number of migraine hours, *Reported Migraine Attacks* is replaced with *Reported Migraine Hours* in the calculations described above. From that, the average length of headache episodes and migraine attacks is calculated as the monthly hours with headache or migraine divided by the number of monthly headache episodes or migraine attacks, respectively. Patients with no migraine attacks/headache episodes are included with an average length of 0 for the month.

19.1.1.5 Monthly Days with Acute Migraine Medication Usage and MMDs/MHDs with Acute Medication Usage

In the evening eDiary, patients are asked each day to fill out whether they used any of the following medications during that day: Ergotamine, triptan, analgesic, opioid, or combination analgesic. A day where the patient answers that they took any of those in the evening eDiary is considered a day with use of acute migraine medication.

The number of days with acute migraine medication usage is then derived for each 4-week period using the imputations described in Section 19.1.1.1 and replacing *Reported Migraine Days* with *Reported Acute Migraine Medication Days* everywhere as well as replacing *Reported eDiary Days* with *Reported Evening eDiary Days*, where a "*Reported Evening eDiary Days*" is defined as any day where the evening eDiary has been filled out.

Similarly, the number of days with each of the medication types taken will be derived as well as the number of days with ergotamine and triptan use.

Additionally, the monthly migraine days/monthly headache days with acute medication usage will be derived. This is derived using the answer to "*Did you take any medications to treat this headache*?" in the headache diary. The question is asked when a patient is ending a headache. Thus, a migraine/headache day with acute medication usage is defined as a migraine/headache day with the extra condition that this question has been answered as "Yes". In case of a migraine/headache with acute medication usage spanning multiple days, all the days will be counted as a migraine/headache day with use of acute medication.

19.1.2 Patient Global Impression of Change (PGIC)

The PGIC is a single patient-reported item reflecting the patient's impression of change in their disease status since the start of the study (that is, in relation to activity limitations, symptoms, emotions, and overall quality of life).

The item is rated on a 7-point scale ranging from 1 (very much improved) to 7 (very much worse).

19.1.3 Most Bothersome Symptom (MBS)

The Investigator will verbally obtain the most bothersome symptom associated with the patient's migraines during the Screening Visit. Patients will be asked to rate the improvement in this symptom from screening on a 7-point scale identical to the scale used for the PGIC, i.e. the scale ranges from 1 (very much improved) to 7 (very much worse).

The MBS areas include: nausea, vomiting, sensitivity to light, sensitivity to sound, mental cloudiness, fatigue, pain with activity, mood changes, and other.

19.1.4 Headache Impact Test (HIT-6)

The HIT-6 (v1.0)⁷ is a Likert-type, self-reporting questionnaire designed to assess the impact of an occurring headache and its effect on the ability to function normally in daily life. The HIT-6 contains 6 questions, each item is rated from "never" to "always" with the following response scores: never = 6, rarely = 8, sometimes = 10, very often = 11, and always = 13. The total score for the HIT-6 is the sum of each response score and ranges from 36 to 78. The life impact derived from the total score is described as followed: Severe (≥ 60), Substantial (56-59), Some (50-55), Little to None (≤ 49).

19.1.5 Migraine-Specific Quality of Life Questionnaire Version 2.1 (MSQ v2.1)

The MSQ v2.1⁸ is a patient-reported outcome designed to assess the quality of life in patients with migraine. It consists of 14 items covering three domains: role function restrictive (7 items); role function preventive (4 items); and emotional function (3 items). Each item is scored on a 6-point scale ranging from 1 (none of the time) to 6 (all of the time).

The items going into each domain⁹ are specified in Panel 6.

Each item score is mapped from the recorded value of the item as shown in Panel 7.¹⁰

For each domain, the score is derived from the final item values by summing the scores from items within each domain and transforming the summed scores as shown in Panel 8.

Domain	Item number	Abbreviated content
Role function restrictive	1	interfered with how well you dealt with family, friends, and others
	2	interfered with your leisure time activities such as reading or exercising
	3	had difficulty in performing work or daily activities
	4	kept you from getting as much done at work or at home
	5	limited your ability to concentrate on work or daily activities
	6	left you too tired to do work or daily activities
	7	limited the number of days you felt energetic
Role function preventive	8	canceled work or daily activities
	9	needed help in handling routine tasks
	10	stopped work or daily activities
	11	not able to go to social activities
Emotional function	12	felt fed up or frustrated
	13	felt like a burden on others
	14	afraid of letting others down

Panel 6 MSQ v.2.1 Domains

Panel 7 MSQ v.2.1 Item Values

Response categories	Precoded item value	Final item value
None of the time	1	6
A little bit of the time	2	5
Some of the time	3	4
A good bit of the time	4	3
Most of the time	5	2
All of the time	6	1

Panel 8 Derivation of MSQ v.2.1 Domain Scores

Domain	Sum of item scores range	Derivation
Role function restrictive	7 to 42	(Summed score – 7)*100/35
Role function preventive	4 to 24	(Summed score -4)*100/20
Emotional function	3 to 18	(Summed score – 3)*100/15

19.1.6 Euroqol 5 Dimension – 5 Levels (EQ-5D-5L)

The EQ-5D-5L¹¹ is a patient-reported assessment designed to measure the patient's wellbeing. It consists of 5 descriptive items (mobility, self-care, usual activities, pain/discomfort, and depression/anxiety) and a visual analogue scale (VAS) of the overall health state. Each descriptive item is rated on a 5-point index ranging from 1 (no problems) to 5 (extreme problems) and a single summary index (from 0 to 1) can be calculated.

The VAS is scored separately and ranges from 0 (worst imaginable health state) to 100 (best imaginable health state).

19.1.7 Health Care Resource Utilization (HCRU)

Migraine-specific healthcare resource utilization information will be collected in terms of outpatient health care professional visits (number of visits to doctor/genral practitioner and number of visits to a specialist), number of emergency room visits, number of hospital admissions, as well as number of overnight hospital stays during the past 4 weeks.

The items from the questionnaire will be analyzed separately.

19.1.8 Work Productivity and Activity Impairment: Migraine (WPAI:M)

The WPAI¹² is a patient self-rated scale designed to provide a quantitative measure of the work productivity and activity impairment due to a specific health problem (WPAI:M). The WPAI assesses activities over the preceding 7 days and consists of 6 items: 3 items assess the number of hours worked, the number of hours missed from work due to the patient's condition, or due to other reasons, and 2 visual numerical scales to assess how much the patient's condition affects their productivity at work and their ability to complete normal daily activities.

The derivation of the WPAI:M sub-scores¹³ is given in Panel 9, where Q1-Q6 refers to question 1-6 in the questionnaire. If both Q2 and Q4 has a score of 0 then both the Absenteeism and the Work productivity loss sub-scores are set to missing.

Sub-score	Description	Derivation
Absenteeism	Percent work time missed due to migraine	100*Q2/(Q2 + Q4)
Presenteeism	Percent impairment while working due to migraine	100*Q5/10
Work productivity loss	Percent overall work impairment due to migraine	$100 * \left(\frac{Q2}{Q2 + Q4} + \left(1 - \frac{Q2}{Q2 + Q4}\right) * \frac{Q5}{10}\right)$
Activity impairment	Percent activity impairment due to migraine	100*Q6/10

Panel 9 Derivation of WPAI:M sub-scores

19.2 Assigning Data to Visits

See Section 4.2 for definition of Baseline values.

19.2.1 Clinical Outcome Assessments (COAs) - Scales

For treated patients withdrawing prior to Week 24, the withdrawal visit scheduled 12 weeks after the last IMP infusion will also include efficacy evaluations (PGIC, MBS, HIT-6, MSQ, EQ-5D-5L, HCRU, and WPAI:M). These assessments will be assigned to either Visit 5 or Visit 8 according to when the patient was withdrawn as follows:

- For patients withdrawing prior to Visit 5, the assessments from the Withdrawal Visit will be assigned to nominal Visit 5
- For patients withdrawing after Visit 5 (but prior to Visit 8), the assessments from the Withdrawal Visit will be assigned to nominal Visit 8.

Unscheduled visits will not contain assessments of the COAs mentioned above. In relation to the nominal visits post-Baseline, a patient can complete their COAs 3 days before the visit. In case of duplicate scale assessments in relation to a nominal visit, i.e. if a patient fills out the scales 3 days before the visit and the visit is postponed afterwards implying that the patient has to complete the COA again, the latest assessment will be used.

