6.6 Unblinding Procedures

Pharmacovigilance, H. Lundbeck A/S, and the investigator or the pharmacist (if applicable), and the DMC will have access to the unblinded information for the double-blind treatment for each patient. Access to these details will be via IRT.

The IRT unblinding procedure is described in the IRT User Guide.

The investigator may only break the code for a patient if knowledge of the IMP is necessary to provide optimal treatment to the patient in an emergency situation. If possible, the investigator must consult the CRA in some cases it may be the medical monitor before breaking the code. The investigator must record the date and reason for breaking the code on the *IMP Code Break Form*. If the emergency situation was an adverse event, it must be recorded on an *Adverse Event Form*. The CRA (in some cases it may be the medical monitor) must be notified immediately. The IRT will capture the date and time of the code break call. Information on the allocated treatment will be provided during the call and by fax or email, depending on availability/preference. When the code is broken for a patient, the patient must be immediately withdrawn from the study. If this occurs during a visit, the investigator must

complete the visit as a Withdrawal Visit; otherwise, the patient will be asked to attend a Withdrawal Visit 12 weeks after his/her last dose of IMP.

6.7 **Post-study Access to IMP(s)**

Patients in the study will have access to appropriate medical care after they complete or withdraw from the study.

7 Concomitant Medication

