8.9 Withdrawal Visit

Patients who withdraw from the study will be asked to attend a Withdrawal Visit, if at all possible. The visit must be scheduled 12 for weeks after the last dose of IMP after withdrawal.

As the Withdrawal Visit will be scheduled 12 weeks after the last dose of IMP, this visit will also serve as a Safety Follow-up Visit for all withdrawn patients (section 8.10). Patients who withdraw prior to Week 24 will undergo additional efficacy evaluations, thus for these patients the Withdrawal Visit will also serve as an Efficacy Follow-up Visit.

At the Withdrawal Visit, the patient must be assisted with the closeout of the eDiary.

No new information will be collected from patients who withdraw from the study, except information collected in relation to the scheduled Withdrawal Visit or needed for the follow-up of adverse events (section 10.5).

The reason for withdrawal must be recorded in the eCRF.

For a patient who withdraws consent:

- if the patient withdraws consent during a visit and then agrees to it being the final visit, the investigator will complete the visit as a Withdrawal Visit and all the data collected up to and including that visit will be used
- if the patient withdraws consent during a telephone conversation, the investigator will ask the patient if they will attend a Withdrawal Visit 12 weeks after their last dose. If the patient:
 - agrees to attend a Withdrawal Visit, all the data collected up to and including that visit will be used
 - refuses to attend a Withdrawal Visit, the investigator should attempt to follow the patient's safety and future treatment; any information collected will only be recorded in the patient's medical records
- if the patient explicitly requests that the patient's data collected from the time of withdrawal of consent onwards not be used, this will be respected

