The patient will receive IMP starting from the Baseline Visit to follow a dosing schedule with IV infusions every 12 weeks with either eptinezumab or placebo over 30 minutes (+15).

At Visit 8 patients will enter the Extension Period. Patients who were assigned to placebo in the Placebo-controlled Period will be randomly allocated to one of two treatment groups: eptinezumab 300 mg or eptinezumab 100 mg with a ratio of 1:1. Patients assigned to eptinezumab 300 mg or eptinezumab 100 mg in the Placebo-controlled Period will continue on their original assignments.

An overview of the study is presented in Panel 2 and the scheduled study procedures and assessments are summarized in Appendix II. See also the *Clinical Study Protocol* for further details on the study design.

Panel 2 Study Design

For patients who withdraw, except for those who withdraw their consent, a Withdrawal Visit will be scheduled 12 weeks after the last dose of IMP. The withdrawal visit will include Safety Follow-up evaluations and will therefore also serve as a Safety Follow-up Visit.

For patients who withdraw prior to Week 24 the Withdrawal Visit will allow for eDiary closeout and for a final assessment of scales not based on the eDiary. Patients are expected to complete their eDiary until this Withdrawal Visit unless the patient withdraws consent.

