19.2.2 Safety Variables

Laboratory Tests and ECG

Assessments of laboratory tests and ECGs at unscheduled visits and withdrawal visits will be assigned to a nominal visit in the Placebo-controlled Period according to the visit windowing specified in Panel 10 for patients in the APTS. Assessments for patients not receiving any infusions of IMP will be assigned to Visit 2 (Baseline). For patients receiving an infusion of

IMP in the Extension Period, assessments of laboratory tests and ECGs at unscheduled visits and withdrawal visits will be assigned to a nominal visit in the Extension Period according to the visit windowing specified in Panel 11.

Panel 10 Visit Windows for Placebo-Controlled Period – Laboratory tests, ECG

Nominal Visit Number	Nominal Visit Week	Nominal Visit Day	Time Window
V1 (Screening Visit)	-4	-28	NA
V2 (Baseline Visit)	0	0	NA
V5	12	84	After start of first IMP infusion to day 126
V8	24	168	Day 127 to start of Visit 8 IMP infusion

Panel 11 Visit Windows for Extension Period – Laboratory tests, ECG

Nominal Visit Number	Nominal Visit Week	Nominal Visit Day	Nominal Visit Day Relative to Visit 8 IMP Infusion	Time Window Relative to Visit 8 IMP Infusion
V11	36	252	84	After start of Visit 8 IMP infusion to day 126
V14	48	336	168	Day 127 to day 210
V17	60	420	252	Day 211 to day 294
V20	72	504	336	> 294

Vital signs will be assessed before and after infusion at nominal visits. For unscheduled or withdrawal visit assessments of vital signs, the values will be assigned a nominal visit according to Panel 12 and Panel 13.

Nominal Visit Number	Nominal Visit Week	Nominal Visit Day	Time Window
V1 (Screening Visit)	-4	-28	NA
V2 (Baseline Visit) pre-dose	0	0	NA
V2 (Baseline Visit) post-dose	0	0	After start of first IMP infusion to day 42
V5 pre-dose	12	84	Day 43 to start of V5 IMP infusion
V5 post-dose	12	84	After start of V5 IMP infusion to day 126
V8 pre-dose	24	168	Day 127 to start of Visit 8 IMP infusion

Panel 12 Visit Windows for Placebo-Controlled Period – Vital Signs

Nominal Visit Number	Nominal Visit Week	Nominal Visit Day	Nominal Visit Day Relative to Visit 8 IMP Infusion	Time Window Relative to Visit 8 IMP Infusion
V8 post-dose	24	168	0	After start of V8 IMP infusion to day 42
V11 pre-dose	36	252	84	Day 43 to start of V11 IMP infusion
V11 post-dose	36	252	84	After start of V11 IMP infusion to day 126
V14 pre-dose	48	336	168	Day 127 to start of V14 IMP infusion
V14 post-dose	48	336	168	After start of V14 IMP infusion to day 210

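### Withdrawal Visit questionnaires are dated by when the patient withdrew, so in a few off-schedule cases an earlier score can be analysed as Week 12 or Week 24

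*SAP*

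**What the plan says.** SAP 19.2.1 covers treated patients who withdraw before Week 24. It first states that "the withdrawal visit scheduled 12 weeks after the last IMP infusion will also include efficacy evaluations" (PGIC, MBS, HIT-6, MSQ, EQ-5D-5L, HCRU and WPAI:M). It then gives the rule: "These assessments will be assigned to either Visit 5 or Visit 8 according to when the patient was withdrawn as follows". Withdrawal before Visit 5 leads to nominal Visit 5; for the rest, "For patients withdrawing after Visit 5 (but prior to Visit 8), the assessments from the Withdrawal Visit will be assigned to nominal Visit 8". There is no limit on the day of assessment, and neither branch names withdrawal at Visit 5 itself.

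The 12-week timing is repeated in SAP section 2, which exempts patients who withdraw consent, and in Protocol 8.9: "As the Withdrawal Visit will be scheduled 12 weeks after the last dose of IMP, this visit will also serve as a Safety Follow-up Visit".

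The protocol also provides two routes off that schedule. Under 8.9, if consent is withdrawn during a visit and the patient agrees to make it the last one, "the investigator will complete the visit as a Withdrawal Visit and all the data collected up to and including that visit will be used". Under 6.6, if the code is broken during a visit, the investigator must "complete the visit as a Withdrawal Visit; otherwise, the patient will be asked to attend a" visit set 12 weeks after the last dose.

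For laboratory tests and ECGs the SAP works differently. Under 19.2.2, results from unscheduled and withdrawal visits "will be assigned to a nominal visit in the Placebo-controlled Period according to the visit windowing specified in Panel 10", that is, by study day. Vital signs have day windows of their own.

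**The concern.** The rule uses the date of withdrawal as a stand-in for the date of assessment. The two agree only if the Withdrawal Visit really happens 12 weeks after the last infusion and if everyone leaving after Visit 5 was infused there. Where either condition fails, a score from an earlier week is filed under Week 12 or Week 24.

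Such a score enters the repeated-measures model as an on-time observation. Week 12 HIT-6 is a key secondary endpoint in the testing strategy. Week 24 HIT-6, PGIC, MSQ, EQ-5D-5L VAS and WPAI are secondary endpoints analysed with the same type of model. A patient who leaves after Visit 5 uninfused would in effect have a score from about Week 12 carried forward to Week 24, in a model meant to leave that cell missing. The placebo-based multiple imputation for HIT-6 (SAP 12.4.4) would not correct this, because it fills only missing values.

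**Working it through.** **Inputs.** Nominal days are 84 for Visit 5 and 168 for Visit 8 (SAP Panel 10), which matches 12 × 7 = 84 and 24 × 7 = 168. Infusions in the Placebo-controlled Period are at Visit 2 (day 0) and Visit 5 (day 84, window ±2). The Withdrawal Visit is due on the day of last infusion + 84, window +2 (Protocol Panel 2).

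**Usual path.** Withdrawal Visit day = day of last infusion + 84, plus 0 to 2.
- First infusion only: 0 + 84 = day 84 to day 86. Label day 84, gap 0 to 2 days.
- Second infusion on day 82 to 86: 82 + 84 = day 166 to 86 + 84 + 2 = day 172. Label day 168, gap at most 4 days.

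So the rule gives the right label by design for patients who follow the schedule.

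**Exceptions.** Here the Withdrawal Visit falls on day d, and the gap in weeks = (label day − d)/7. The days are illustrative.

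| Day of Withdrawal Visit | Questionnaire label | Gap (weeks) | Laboratory/ECG label (Panel 10) |
|---|---|---|---|
| 28 | Week 12 | (84 − 28)/7 = 8.0 | Visit 5 |
| 56 | Week 12 | (84 − 56)/7 = 4.0 | Visit 5 |
| 86, after Visit 5 | Week 24 | (168 − 86)/7 = 11.7 | Visit 5 |
| 100 | Week 24 | (168 − 100)/7 = 9.7 | Visit 5 |
| 140 | Week 24 | (168 − 140)/7 = 4.0 | Visit 8 |

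Visit 5 attended, no infusion, then withdrawal: the last infusion is day 0, so the Withdrawal Visit is due on day 84. The rule labels it day 168, and the gap is (168 − 84)/7 = 12.0 weeks.

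**Which endpoint is hit.** Only rows before Visit 5 put an early score at Week 12. All the others go to Week 24.

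**Size.** The documents do not say how often this happens. Assume a share of 0.5-2% of an arm of 280 and a misdated score that differs by 4 points from the true one.
- Patients per arm: 0.005 × 280 = 1.4 to 0.02 × 280 = 5.6.
- Shift in the arm mean: 0.005 × 4 = 0.02 to 0.02 × 4 = 0.08 points, on a scale running from 36 to 78.

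This pools Week 12 and Week 24 cases, so it overstates the shift at either one. The difference between arms moves less still if the arms are affected alike.

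**The case against.** The strongest reply is that the rule is right by construction and the exceptions are narrow. Much of this stands. Visits 3, 4, 6 and 7 are phone contacts, and a patient who withdraws consent by phone is asked to come 12 weeks after the last dose, which is on schedule. An early on-site Withdrawal Visit therefore generally needs an unscheduled visit. Protocol 8.8 lists only laboratory tests, ECG and vital signs for those, and SAP 19.2.1 says they will not contain these scales. Code break is reserved for emergencies. Since SAP 7.2 equates leaving treatment with leaving the study, most patients not infused at Visit 5 would withdraw at that visit rather than after it. The Week 24 scales lie outside the testing strategy and carry nominal p-values only. The contrast with laboratory data is also limited: before Visit 5 both rules give the same label.

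Two parts do not carry the weight put on them. An unscheduled visit that is completed as the Withdrawal Visit is no longer governed by the statement that unscheduled visits lack questionnaires, and Protocol 8.9 says its data are used. The HIT-6 estimand does use available values whatever the reason for withdrawal, but that justifies keeping the score, not moving it to another week. SAP 12.3.3 also foresees infusions ended without withdrawal, so leaving later without a second infusion remains possible.

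A reader might infer that withdrawal-visit scores are misdated as a matter of course. The documents do not support that: three places set the visit 12 weeks after the last dose, and on that path the label and the date agree.

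**Conclusion.** The point holds as a minor one. For a small group that the documents themselves make possible, the stated rule gives the wrong week, by up to about 12 weeks. For everyone on schedule it is correct. Withdrawal at Visit 5 is left unassigned.

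The exposure is mainly at Week 24. Key secondary HIT-6 at Week 12 is directly affected only by off-schedule Withdrawal Visits before Visit 5. The HIT-6 responder endpoints are less sensitive, since SAP 12.5 carries the last value forward to Week 12 or Week 24 anyway, and HCRU is only tabulated. The 0.02-0.08 point range rests wholly on the assumed share and the assumed 4-point error. A reader might infer a threat to the HIT-6 conclusion or to the error control; nothing in the documents supports either, and no power or alpha figure changes.

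**What to change.** In SAP 19.2.1, replace assignment by withdrawal time with the following:

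- Assign each Withdrawal Visit scale by its actual assessment day to the nearest visit at which that scale is scheduled: every 4 weeks for HIT-6, EQ-5D-5L, HCRU and WPAI, and their own visits for PGIC, MBS and MSQ.
- State a window narrower than Panel 10. For the four-weekly scales, half the interval (28/2 = 14 days either side) is the natural upper limit. Values outside any window count as missing in the by-visit model.
- State that withdrawal at Visit 5, or after it without a second infusion, fills Week 24 only if the assessment falls in the Week 24 window.
- State that an on-schedule value takes priority over a withdrawal-visit value at the same nominal visit.

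Reusing Panel 10 as it stands would not do. It sends everything up to day 126 to Visit 5, so scores from day 28 or 56 would still be called Week 12. A day-100 score would join a valid Week 12 score, and the duplicate rule in 19.2.1, which keeps the latest assessment, could then let it displace the valid one. The priority for scheduled values is written only under 19.2.2 for safety variables. Under the proposed rule a day-100 HIT-6 goes to Week 16 (12 days away), and a day-100 MSQ, 16 days from Week 12, is missing if the 14-day window is used there too.

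The cost is a short paragraph, minor programming and a few more missing values. Patients on schedule are unaffected. If the Placebo-controlled Period has already been analysed, report the number of patients concerned by arm and repeat the affected analyses under the new rule as a sensitivity analysis.
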